10. DATA MANAGEMENT

Data will be recorded on an eCRF by the Investigator (or designee). The database, data entry and electronic checks will be developed using a Clinical Database Management System. Computerised data cleaning checks will be used in addition to manual review to check for discrepancies and to ensure consistency and completeness of the data. An electronic audit trail system will be used to track all data changes in the database.

Data clarification queries will be generated electronically in order to clarify any issues which arise regarding the data entered into the eCRF and database.

Medical history and AEs will be coded using the Medical Dictionary for Regulatory Activities (MedDRA) dictionary; medications will be coded using the World Health Organisation Drug Dictionary.

10.1. Trial Documentation and Trial Confidentiality

10.1.1. Trial Documentation, eCRFs and Document Keeping

The Investigator must generate and maintain adequate records (subject medical records, eCRFs, source documents) to enable the conduct of this study to be fully documented. Each subject enrolled into the study must have an eCRF completed and the eCRF must be reviewed and signed off by the Investigator. This applies to those subjects who failed to complete the study (even during the pre-surgery period). eCRFs are to be completed either at the time of the subject's visit or as soon as possible after the visit so that they always reflect the latest observations on the subjects participating in the study. The Investigator must verify that all data entries in the eCRFs are accurate and correct. The nature and location of all source documents will be identified to ensure that all sources of original data required to complete the eCRF are known to the investigational staff and are accessible for verification by the clinical monitor. If electronic records are maintained, the method of verification must be discussed with the investigational staff. A source data verification log will be prepared by the CRO. This will describe the proportion of eCRF data that will be verified by the monitor against the subjects' medical records and source data.

The Sponsor recommends that the author of an entry in the source documents be identifiable. Direct access to source documentation (medical records) must be allowed for the purpose of verifying that the data recorded on the eCRF are consistent with the original source data.

If data are recorded directly into the eCRF, there should be, at a minimum, an entry in the medical record that each of the assessments was performed; who performed it and the date it was done.

The eCRF will be compared with the source documents to ensure that there are no discrepancies between critical data. All entries, corrections, and alterations are to be made by the responsible Investigator or an authorised member of the investigational staff.

Data clarification and query resolution will be conducted on an ongoing basis by the monitor and the contract data management company. The Sponsor will have overall responsibility for the data.

The Investigator must be aware of their responsibility to retain subject identification codes in line with regulatory requirements after completion or discontinuation of the

study. If a subject withdraws from the study, then the reason must be noted in the eCRF. If a subject ceases treatment because of an AE, reasonable efforts must be made to clearly document the outcome.

The Investigator will allow authorised Sponsor personnel, auditors and regulatory authorities direct access to the subjects' medical records.

Copies of protocols, eCRF page/printouts, originals of test results, reports, drug dispensing logs, correspondence, records of informed consent or other documents pertaining to the conduct of the study must be kept on file by the Investigator in line with regulatory requirements or for the period of time specified by local law for the preservation of hospital subject documents, whichever is longer. No study documents should be destroyed without prior written agreement between the Sponsor and the Investigator. Where storage at the centre is limited, the Sponsor may make arrangement for documents to be stored at an independent data archiving facility on behalf of the Investigator. Should the Investigator wish to assign the study records to another party, or move them to another location, the clinical trial monitor must be consulted.

10.1.2. Confidentiality of Trial Documents and Subject Records

The Investigator must ensure the subjects' anonymity is maintained. On eCRFs or other documents submitted to the Sponsor (or designee), subjects must NOT be identified by their names but by an identification code (usually their study number). The Investigator will be responsible for maintaining a separate log of subjects' codes, names and unique identifiers. This log will be maintained as required by applicable regulatory requirements. Documents not for submission to the Sponsor or designee, e.g., subjects' written consent forms, must be maintained by the Investigator in strict confidence. Genetic testing will occur prior to surgery but to ensure subject confidentiality, the distribution of these data will be carefully controlled.

11. STATISTICAL ANALYSIS PLAN

A detailed statistical analysis plan (SAP) will be produced after having finalised the protocol and before the database is locked prior to analysis.

11.1. Sample Size

As this is a FIH exploratory Phase I/II study, no formal sample size has been calculated.

11.2. Population for Analysis

Two analysis sets will be defined. The Safety Analysis Set (SAF) will include all subjects who have undergone surgery and received GT005. The SAF will be used for analysis of safety and laboratory data. The Full Analysis Set (FAS) will include all subjects in SAF who have baseline and at least one post-baseline value of GA area size via FAF in the study eye. The FAS will be used for analysis of efficacy data.

11.3. Statistical Analysis

The detailed statistical analyses will be outlined in the SAP.

The main analysis will be performed at the conclusion of the study (Week 240), after which a clinical study report (CSR) will be prepared. Interim analyses may be considered to help inform internal development decision points for GT005, in which case the details will be pre-specified in the SAP prior to conducting the analysis. Additionally, a safety focused analysis will be conducted to enable the independent data review by a DSMB after three subjects in Cohorts 1 to 3 and Cohort 5 have completed the 5-week post-surgery visit. Additional DSMB meetings may be held as needed or as requested by the DSMB members. Full details can be found in the DSMB Charter.

Analyses of data involving the Orbit SDS is US-specific.

For the main statistical analysis and CSR, all efficacy (anatomical and functional visual outcomes) and safety data will be listed and summarised using descriptive statistics by dose and route of administration, and by assessment (Visits 1 to 8). The Long-term follow-up data (Visits 9 to 13) will be reported separately using descriptive statistics by dose and route of administration and by assessment. Additionally, for all ocular evaluations and tests, and ocular AEs, where appropriate these will be additionally presented by eye (Treated [Study Eye]/Untreated [Fellow Eye]). The descriptive summary for the categorical variables will include subject counts (n) and percentages and, if appropriate, frequency of events. The descriptive summary for the continuous variables will include counts (n), means, medians, standard deviations and minimum and maximum values. Where possible, all data from subjects who withdraw prematurely from the study will be included in any presentations. Further details on the handling of withdrawals and/or missing data will be specified in the SAP.

Subgroup analyses will be performed, if appropriate, to evaluate some of the efficacy endpoints across subgroups defined by genetic classification: e.g., a rare variant resulting in CFI haploinsufficiency and those without.

Graphical displays appropriate to the types of data may be used to present any important findings.

Any deviations from the planned analyses detailed in the protocol will be documented in the SAP and final CSR. If the study is prematurely discontinued, all available data will be listed and a review will be carried out to determine which statistical analyses are considered appropriate.

11.3.1. Demographics and Baseline Characteristics:

Surgical details and measures at baseline including: demographics, medical/surgical history, concomitant medication, laboratory safety, and urine pregnancy testing will be summarised descriptively by dose and route of administration. No formal comparisons between Cohorts will be made. Assessments made at screening/baseline and also post-surgery will only be included in their respective safety and efficacy tables, together with post-baseline assessment values.

A medication given prior to the injection of study drug during surgery will be classified as a prior medication. A medication given with or after the injection of study drug will be classified as concomitant. Prior medications continuing during the study will be labelled accordingly in the listings.

Verbatim medical/surgical history terms will be coded (to preferred terms) using terminology from MedDRA. Medications will be coded using the World Health Organisation Drug Dictionary to Anatomical Therapeutic Chemical classification level 2 (therapeutic main group) and preferred term.

Additionally, the last visual acuity values measured using the BCVA ETDRS prior to surgery will be presented with the baseline data by dose and route of administration and by eye (Treated [Study Eye]/Untreated [Fellow Eye]). Genetic testing will also occur prior to surgery but to ensure subject confidentiality, the distribution of these data will be carefully controlled. Further details of the procedures required for maintaining the subject's genetic profile confidentiality will be discussed in greater detail in the SAP.

11.3.2. Efficacy

Efficacy assessments to evaluate the anatomical and functional visual outcomes involve: GA area size (via FAF), [REDACTED]
[REDACTED], macular mean sensitivity via Microperimetry, [REDACTED]

For continuous efficacy variables the change from baseline will be derived and presented together with actual values over time (visit) by dose and route of administration and by eye (Treated [Study Eye]/Untreated [Fellow Eye]). Categorical variables from any ocular evaluations will be presented by classification over time (visit) by dose and route of administration and by eye (Treated [Study Eye]/Untreated [Fellow Eye]).

The GA area size data will be compared to historical data on natural disease progression, including pre-treatment data from FOCUS subjects if available.

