8. Have received any investigational product for the treatment of GA within the past 6 months or 5 half-lives (whichever is longer), other than nutritional supplements such as the age-related eye disease study (AREDS) formula
9. Have received a gene or cell therapy at any time
10. Have a contraindication to the specified protocol corticosteroid regimen
11. Are unwilling to use two forms of contraception (one of which being a barrier method) for 90 days post-dosing, if relevant
12. Active malignancy within the past 12 months, except for: Appropriately treated carcinoma in situ of the cervix, non-melanoma skin carcinoma, or prostate cancer with a stable prostate-specific antigen (PSA) ≥ 12 months
13. Have any other significant ocular or non-ocular medical or psychiatric condition which, in the opinion of the Investigator, may either put the subject at risk or may influence the results of the study
14. Cohorts 5 to 7 only: presence of metallic objects or implanted stimulator devices in or near the head, including cochlear implants, deep brain stimulators, vagus nerve stimulators, and other implanted electrodes or stimulators

DOSE/ROUTE/REGIMEN:

The study drug is supplied to the surgical site as a vial of frozen sterile liquid.

GT005 is an aqueous suspension of recombinant AAV2 vector particles in [REDACTED]

[REDACTED] GT005 is administered at ambient temperature as a single subretinal injection into the macula of the study eye.

Surgical procedure

GT005 will be administered subretinally via the transvitreal procedure for Cohorts 1 to 4, an approach which is based on publicly available methodology. GT005 will be administered subretinally via a suprachoroidal cannulation with the Orbit SDS for Cohorts 5 to 7 (US sites only). All Cohorts will be treated by an appropriately qualified vitreoretinal surgeon in an operating room under local anaesthesia. Other anaesthetic options will be considered by the surgeon as appropriate for the subject. The total duration of the surgery is about 1 hour. The detailed procedure is described in the relevant Surgical Manuals.

In brief:

Cohorts 1 to 4

[REDACTED]

Cohorts 5 to 7 (US sites only)

[REDACTED]

DURATION OF TREATMENT AND FOLLOW-UP

Subjects will receive a single subretinal injection and will be followed for up to 240 weeks (5 years) post-dosing.

REFERENCE TREATMENT:

Only one eye will be treated in the study and the untreated fellow eye will be the comparator.

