1.6.1.2. Risks Associated with the Surgical and Study Procedure

1.6.1.2.1. Transvitreal Surgery (Cohorts 1 to 4; US and United Kingdom [UK])

The transvitreal surgical technique employed for this clinical study has been developed and successfully used for the Choroideremia subretinal gene therapy clinical studies [MacLaren 2014; Xue 2017]. Risk mitigations strategies have also been developed to minimise foveal or retinal stretch during vector delivery, or prevent post-surgical ocular inflammation. A careful pre-operative assessment of the retina is done as part of surgical planning, with a range of visual function tests as well as retinal imaging to determine the functional and structural integrity of the targeted retina. The risks include:

Intraocular inflammation

A **transient visual loss** may be observed in the first days post-surgery due to the bleb related foveal detachment. This can be minimised by avoiding injecting into areas of retinal thinning and by not detaching the fovea, if it is deemed not necessary, and by leaving the contralateral (and best) eye untreated. Retinal detachment usually

regresses over 24 hours when the subretinal fluid resolves and retinotomy self-seals. Structural recovery of the retina following iatrogenic detachment of the macula generally occurs within one month [Xue 2017]. [REDACTED]

[REDACTED]

[REDACTED]

[REDACTED]

[REDACTED]

[REDACTED]

[REDACTED]

[REDACTED]

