##### 3.1.1. Study days and visit windows

Study day is defined as the number of days relative to the date of the subretinal injection with the study drug. For a particular date, study day will be calculated as follows:

- for dates on or after the date of study treatment: Study day = Assessment date – Date of treatment administration + 1;
- for dates prior to the date of administration of study treatment: Study day = Assessment date – Date of treatment administration.

Baseline values are defined as values from the last assessment prior to surgery for the study treatment administration. All data collected after the treatment administration are defined as post-baseline.

The end of study date is the date when a patient completes or discontinues the study. For reporting data by visit in outputs, the end of study visit will be allocated to the actual (reported) visit number. If the end of study date is not on a scheduled visit, then the end of study visit will be allocated, based on study day, to the closest future scheduled study visit.

For scheduled visits, the analysis visits will be the actual (reported) visits.

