### 3.7. Efficacy analyses

Efficacy analyses will be conducted using the FAS by treatment dose and route of administration.

**GA area (mm^2)** change from baseline in the study eye as assessed by FAF will be presented in spaghetti plots and in a summary by visit table. It will also be summarized in a table and line plots as least-squares means with 95% CI by visit using MMRM model with fixed effects for treatment (defined as dose and route of administration), study visit, baseline GA area (mm^2), treatment by visit interaction and visit by baseline GA area interaction.

**Square root of GA area (mm)** change from baseline in the study eye will be presented in spaghetti plots and in a summary by visit table. It will also be summarized in a table and line plots as least-squares means with 95% CI by visit using MMRM model with fixed effects for treatment, study visit, square root of baseline GA area (mm), treatment by visit interaction and visit by square root of baseline GA area (mm) interaction. MMRM analysis will be repeated for CFI rare variant subgroups and [REDACTED] by replacing in the model treatment with subgroups of interest.

For MMRM analysis an unstructured covariance matrix will be used to model the within-patient error. If an MMRM model with an unstructured covariance matrix does not converge, a more restricted covariance matrix can be considered in the following order until convergence is reached: first-order autoregressive, Toeplitz, compound symmetry and variance components.

Additionally, scatter plots with linear trend lines for square root of GA area size (mm) change from baseline at the target analysis visit vs. last observed CFI levels before the target analysis visit in the vitreous and aqueous samples will be generated by treatment groups.

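### GA growth is estimated only from a pre-surgery image while the comparators are unoperated, so a one-off surgical change in measured area, if there is one, would not be separated from growth

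*Protocol*

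**What the plan says.** Protocol 11.3.2 sets the measure: "For continuous efficacy variables the change from baseline will be derived and presented together with actual values over time (visit", split by dose, route and eye. SAP 3.1.1 fixes the starting point: "Baseline values are defined as values from the last assessment prior to surgery for the study treatment administration". Autofluorescence is not among the scheduled pre-surgery assessments, so for GA this is normally the screening image. SAP 3.7 states that GA area "change from baseline in the study eye as assessed by FAF will be presented in spaghetti plots and in a summary by visit table". It then plans least-squares means with 95% CI by visit, in mm² and on the square-root scale, from an "MMRM model with fixed effects for treatment (defined as dose and route of administration), study visit", baseline value and the interactions with visit. The readable text contains no term or contrast that starts from a post-surgery image.

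The Protocol has two comparators. The synopsis (Reference Treatment) says "Only one eye will be treated in the study and the untreated fellow eye will be the comparator". Section 11.3.2 adds: "The GA area size data will be compared to historical data on natural disease progression, including pre-treatment data from FOCUS subjects if available". Section 6.6 confirms that every participant receives GT005, so there is no surgery-only group.

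On the surgery, Protocol 1.6.1.2.1 says: "Structural recovery of the retina following iatrogenic detachment of the macula generally occurs within one month". Autofluorescence is scheduled at Weeks 5, 12, 24, 36 and 48 (Table 2) and from Week 72 onward (Table 3).

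**The concern.** The hoped-for benefit in Protocol 1.6.2 is slower extension of the atrophy, which is a rate. The comparators supply a rate without surgery. The treated eye's change from baseline contains growth plus whatever the procedure did to the measured area between the screening image and the first post-dose image. A step of that kind does not fade. It enters the least-squares mean at every later visit at full size, and only its share of the total shrinks as growth accumulates.

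Against an unoperated eye or natural-history data, an upward step could cover a real slowing and a downward step could look like one. Within one delivery route, a step common to all doses cancels between doses. It need not cancel between the transvitreal and Orbit routes: Protocol 1.5 says Orbit was developed to improve on the transvitreal safety profile, so equal procedural effects cannot be presumed.

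No hypothesis is tested (SAP 3.1), so these estimates and intervals are the efficacy evidence. Protocol 11.3 allows interim looks to inform development decisions.

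**Working it through.** The documents give no growth rate, SD or surgical step, so the plan has no figure to reproduce. Every input below is an assumption except the visit weeks and screening limits.

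**Inputs from the documents.** First post-dose autofluorescence is at Week 5 (−7/+3 days), so the window opens at Week 4. The screening image may be up to 8 weeks old at dosing, or 12 if screening is extended. Autofluorescence is repeated only beyond 12 weeks after a deferral (Protocol 7.1).

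**Assumed inputs.** Square-root growth 0.30 mm/year (range 0.2 to 0.4); step 0.05 to 0.10 mm; an 8 mm² lesion to convert to area.

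**Step in area units.** (√8 + 0.05)² − 8 = 2 × 2.828 × 0.05 + 0.0025 = 0.29 mm². For 0.10 mm: 2 × 2.828 × 0.10 + 0.01 = 0.58 mm².

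**Step as a share of growth from baseline to Week 48 or Week 96, at 0.30 mm/year:**

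| Age of baseline image at dosing | Weeks covered at Week 48 | Growth (mm) | 0.05 mm step | 0.10 mm step |
|---|---|---|---|---|
| 0 weeks | 48 | 0.30 × 48/52 = 0.277 | 18% | 36% |
| 8 weeks | 56 | 0.323 | 15% | 31% |
| 12 weeks | 60 | 0.346 | 14% | 29% |

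At Week 96 with no lag, growth is 0.554 mm and the shares are 9% and 18%. Over 0.2 to 0.4 mm/year with no lag, the shares are 14% to 54% at Week 48 and 7% to 27% at Week 96.

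**Separate check in mm².** Let g be growth per year, e the true slowing and s the step. Then:

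- treated eye at week t: s + (1 − e) × g × t/52
- unoperated comparator: g × t/52
- treated eye counted from Week 5: (1 − e) × g × (t − 5)/52

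The step that exactly hides a slowing e is e × g × t/52. For g from 1.0 to 2.5 mm²/year at Week 48, this is 0.18 to 0.46 mm² for a 20% slowing and 0.28 to 0.69 mm² for 30%. At Week 96 these double.

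Example with g = 1.5, s = 0.5 and e = 20%:

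- From baseline to Week 48: 0.5 + 0.8 × 1.5 × 48/52 = 1.61 mm² against 1.38 mm². The treated eye looks 16% faster.
- From Week 5 to Week 48: 0.8 × 1.5 × 43/52 = 0.99 mm² against 1.24 mm². The 20% slowing is recovered.

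A step complete by the anchor visit drops out. One still developing does not.

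**Why the early change is not a surgical estimate.** Ordinary growth from baseline to Week 12 spans 12 weeks, or 24 with a 12-week-old image: 0.30 × 12/52 = 0.07 mm to 0.30 × 24/52 = 0.14 mm. That is as large as the assumed step.

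**Precision of the annual rate.** SD = √(0.12² + 2m²/T²), with between-eye rate SD 0.12 mm/year and measurement SD m of 0.03 to 0.08 mm (both assumed). Comparing T = 36/52 (Week 12 to 48) with T = 48/52 gives ratios of 1.05 (m = 0.03), 1.11 (m = 0.05) and 1.18 (m = 0.08).

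**The case against.** The strongest objection is that nothing in the documents says this surgery changes lesion area on autofluorescence. Protocol 1.6.1.2.1 says the detachment usually regresses within 24 hours and that structure generally recovers within a month, about when the first post-dose image is taken. It mentions retinal damage only as one possible cause of worsening vision, which it classes as uncommon. This stands. A reader might infer that the estimates are biased, or that the plan reads surgical change as disease progression. The text supports neither.

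A step would also not be invisible. Actual values, individual-eye plots and visit-specific means all include Week 5, and growth between two post-surgery visits is the difference of two planned means. This stands in part. The interval for that difference needs the covariance between visits, which the per-visit intervals do not supply, and no readable output removes a step.

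Protocol 11.3.2 gives no method for the natural-history comparison, and the readable part of SAP 3.7 gives neither that comparison nor a fellow-eye one for GA. The comparison is therefore not formally tied to the pre-surgery baseline. That is a further gap, and it does not protect against this one.

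Routes are not randomised, entry criteria differ by cohort, and no route contrast is stated. A different step by route is one added reason for caution, not the main one. Finally, parts of SAP 3.7 are blacked out, so the finding covers readable text only.

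**Conclusion.** The point holds as an uncontrolled possibility. The baseline is pre-surgical, both comparators are unoperated, there is no surgery-only group, and no readable analysis gives an interval for growth between two post-surgery visits. If a one-off step exists, it enters every later change-from-baseline mean. At the assumed 0.30 mm/year, a step of 0.05 to 0.10 mm would be roughly 14% to 36% of the Week 48 change. It would be about half that share at Week 96, so longer follow-up dilutes it without removing it. These figures rest on assumed step sizes and growth rates.

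Three stronger readings are not supported: that surgery is known to alter lesion area, that the dose comparison within a route is distorted (a common step cancels), and that the early change measures the surgical effect. GA area is a secondary criterion in a first-in-human study whose primary aim is safety. The change is nevertheless worth making because it is cheap and uses data already scheduled.

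**What to change.** In SAP 3.7, keep the planned change from baseline and add the following:

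1. From the same square-root MMRM, for each dose-by-route group, report the annualised least-squares mean change with 95% CI from Week 12 to Weeks 48, 72 and 96 where data exist. Repeat with Week 5 as the start as a sensitivity analysis. Week 12 is the cautious anchor because the Week 5 window opens at Week 4 and recovery is only generally complete by one month.
2. Report the same post-surgery interval descriptively in fellow eyes with measurable GA. Inclusion criterion 2 requires AMD in that eye but not GA, so the number of such eyes should be shown.
3. Set the post-surgery rate beside the natural-progression rate of Protocol 11.3.2.
4. Show the changes from baseline to Week 5 and to Week 12 separately, labelled as early change that mixes surgery, ordinary growth since the screening image and any early drug effect.
5. State that drug and surgery cannot be fully separated without a surgery-only control. A lasting procedural effect on growth rate would remain in the new contrasts as well.

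The cost is a few contrast statements and a short fellow-eye table, with no new visits. The supplementary Week 12 to 48 rate has the 5% to 18% loss of precision shown above and omits any drug effect before the anchor visit, which is why it supplements the planned estimate and does not replace it.
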